Study Title: Study of Acarbose in Longevity

NCT02953093

IRB Number: 2016-6933

IRB Approval Date: 10/05/2018

Study of Acarbose in Longevity (SAIL)

A. Introduction and Specific Aims:

Acarbose, an FDA approved drug for the treatment of type 2 diabetes, has known effects on glucose metabolism. Evidence from mice indicates that acarbose may prolong lifespan. In humans, acarbose improves inflammatory markers and reduces cardiovascular events. Consequently, acarbose is of interest in clinical translational aging research since it may influence fundamental processes that contribute to age-related diseases. We herein propose an exploratory study to examine the effect of acarbose treatment on the biology of aging in humans. Specifically, we plan to investigate whether treatment with acarbose will restore the gene expression profile of older adults to that of young healthy subjects.

Specific Aims: We propose a 5 month randomized, double blind, placebo-controlled, cross-over study of acarbose treatment in older men (age > 60, n=30), with the following aims:

Specific Aim 1: To assess the effect of acarbose on gene expression profile, with a focus on molecular pathways known or suspected to play a role in aging.

Sub-aim 1: As a secondary analysis, we plan to assess the relationship between changes in gene expression with selected phenotypic variables and biomarkers, including changes in insulin sensitivity and glucose tolerance, vascular function, oxidative stress, inflammation, gut bacteria and/or serum microRNA profiles.

Specific Aim 2: To determine if treatment with acarbose will restore the gene expression profile of older, glucose intolerant men to that of young, healthy subjects.

B. Background and Significance:

Aging is a well-established risk factor for many disabling diseases including diabetes, cardiovascular disease, Alzheimer's disease and cancer. In fact, the risk of death from these causes is dramatically accelerated (100-1000 fold) between the ages of 35 and 85 years. There has been growing interest in understanding common pathways that accelerate age-related diseases, with the goal of therapeutically targeting such pathways to maintain health in older age. Several agents increase lifespan and prevent diseases of aging in animals, but studies in humans are needed.

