Muscle and adipose are key metabolic tissues that undergo significant age-related changes, and play an active role in the pathogenesis of aging. ²⁷⁻²⁹ We are characterizing transcriptional changes with aging in these tissues, and studying the effects of therapeutic interventions. RNA-Seq analysis is being used to identify pathways targeted by candidate anti-aging drugs that have been tested in animals. In addition, we are accumulating a repository of muscle and adipose biopsy samples obtained from young healthy controls to establish a unique biological "fingerprint" for aging in these tissues by comparing changes in gene expression in older adults, post-drug therapy to the profiles of young healthy subjects. This overall approach is supported by a grant from the Glenn Foundation for the Study of the Biology of Human Aging and we are currently analyzing data from two prior studies using metformin and resveratrol. We have gene transcription profiles from RNA seq performed on fat and muscle biopsies from 4 young individuals and plan to recruit up to 30 more young participants under a separate protocol.

As part of our secondary analyses, we also plan to assess changes in microRNA levels in the serum. MicroRNAs (miRNAs) are small, non-coding RNAs that regulate gene expression at a post-transcriptional level. Due to their stability in blood, changes in expression of circulating miRNA might serve as markers for age-related pathologies. Investigators at Einstein have profiled B-lymphocyte miRNA levels in the plasma and have identified microRNA profiles associated with exceptional longevity. We hypothesize that acarbose treatment will alter the expression of circulating miRNAs in a way that may offer insight into anti-aging mechanisms of acarbose. Given the known effects of acarbose on colonic fermentation and composition of gut microbiota we plan to explore changes in gut microbiome using 16s rDNA seq. We plan to correlate changes in transcription (muscle and fat RNAseq), post-translational regulation (miRNA) and gut microbiome with changes in clinical metabolic outcomes and inflammatory biomarkers.

C. Research Methods:

C.1. Study Design & Protocol Summary: We propose a 22-week randomized, double-blind, placebo controlled cross-over study of acarbose in older adults (n=30) with impaired glucose tolerance.

		Treat-			Wash	Treat-		
		ment A			-out	ment b		
	Visit 1	Visit 2 0	Visit 3 4 wks	Visit 4 10 wks	2 wks	Phone call: 12wks	Visit 5 16 wks	Visit 6 22 wks

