Visit 4: At the completion of the 10-week treatment period (up to 4 week titration, 6 week maximum dose) a standard mixed meal test (SMT) will be conducted and muscle and adipose tissue biopsies will be performed, after procedural risks are again explained by the physician performing the muscle and fat biopsies and a Montefiore procedural consent is signed by the participant. Fasting and 2hour blood samples will be collected for analyses noted above. Stool sample tubes will be collected. Vital signs and interval history will be obtained. Subjects will bring unused medication for assessment of adherence. Additional interim safety and/or adherence visits will be conducted if indicated. Instructions to maintain usual diet and activity patterns will be reinforced at each visit. Participants will be given treatment B, and will be instructed to start them after a 2-week washout. The same titration instructions detailed above will be provided to participants. Phone call- After a 2 week washout participants will be reminded to start treatment B with a phone call

Visits 5-6: The procedures in visits 3-4 will be repeated.

C.1.2 Inclusion and Exclusion Criteria:

[figure not shown]
Subjects with impaired glucose tolerance or with mild, untreated diabetes (defined below) based on a screening OGTT will be enrolled. Patients with a prior diagnosis of diabetes may enroll if they are not taking anti-diabetic medications and they meet OGTT criteria. If a participant has had an OGTT within the past year, results of this test may be used to determine eligibility. Given rodent studies demonstrating pronounced effects on males, we plan to recruit males for this small study, with a plan to study females in a subsequent, larger study if effects are seen. Although this approach decreases the generalizability of our initial findings, by increasing the homogeneity of the study population and targeting the gender most likely to benefit, we hope to improve the power to detect a treatment effect in this small, preliminary, study.

Inclusion:

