Adipose Biopsy: An adipose sample will be obtained from the periumbilical region. A small 0.5 cm cutaneous incision will be performed under local anesthesia and 2-6 grams of adipose tissue (which will vary depending on participant's adiposity) will be obtained by aspiration technique. Whole adipose tissue for analysis by rt-PCR will be immediately homogenized in Trizol (Life Technologies, Bethesda, MD) with a Tissumizer homogenizer. Subsequent mRNA extraction and analysis of gene expression (RNA seq) will be performed at Einstein's Sequencing Core Facility using multiplexed 100bp single-end sequencing on an Illumina HiSeq2500.

Remaining fresh adipose biopsy specimens will be immediately digested with collagenase type 1.

C.2.2 Sub-Aim 1: To assess the relationship between changes in gene expression with selected phenotypic variables and biomarkers, including changes in insulin sensitivity and glucose tolerance, vascular function, oxidative stress, inflammation, gut bacteria and/or serum microRNA profiles.

Detailed Methods

Screening OGTT: A 75-gram OGTT will be conducted in the morning following an overnight fast according to standard methods.

Standard Meal Test Protocol: A standard mixed meal challenge, rather than oral glucose challenge, represents a more physiologically relevant stimulus, in that it may more closely mimic metabolic changes experienced by individuals in daily life. Standard meal tests (SMT) with frequent blood sampling and application of mathematical modeling have been used to evaluate insulin sensitivity and insulin secretion, and have been reported to produce results comparable to more invasive and less physiologic tests.^{32, 33} Furthermore, the contribution of the incretin hormones to stimulated insulin secretion is captured, unlike intravenous tests. In our protocol, subjects are studied following an overnight fast and after a test meal of 110g CHO, 20g protein, 20g fat. Blood sampling is performed fasting and 30, 60, 120, and 180 minutes following the meal through an indwelling intravenous catheter and will be used to calculate glucose and insulin AUC. Subjects are

provided with a standard meal to consume at home on the night prior to the next SMT, in order to minimize metabolic variability between tests.

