C.3.2 Statistical analysis and sample size: We plan to enroll up to 30 older male subjects in a cross-over design (30 data points per treatment). Since this is an exploratory study, data obtained will be used to design future interventions that are larger in size and include women, and/or that more specifically investigate pathways that may be affected by acarbose. Data from this study will also be used to estimate effect size and to allow formal power calculations for future, larger studies. Previous studies of gene transcription have demonstrated that effect sizes on gene transcription can be substantial,³⁵ and differential expression can be detected in the same tissues, before and after an intervention in as few as 10-15 individuals.³⁶ Our study of resveratrol confirms the ability to detect differential expression in a sample size of 16, using a crossover design even when clinical effects are modest or negligible. Increasing the sample size to up to 30 will increase the ability to detect transcripts with a lower fold change.

RNA-Seq: Transcriptional profiles will be obtained by the use of the RNA-Seq assay at Einstein's Sequencing Core Facility, specifically using multiplexed 100bp single-end sequencing on an Illumina HiSeq2500. Under a separate protocol, #07-534, we have analyzed transcripts of muscle and adipose tissues obtained from unrelated young (20-30 yo) and we plan to submit another protocol to recruit additional young controls whose transcriptional profiles will further expand our "repository". These analyses will help us further define the parameters of biological transcript changes with aging. These results will provide "proof of concept" and help to set the stage for testing more interventions.

We anticipate $\sim 30M$ reads passing quality control to be aligned to the human genome. The alignment process will be implemented by use of the GSNAP and HTSeq packages – [version date 9/30/18]

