these specifically implement a splice-junction aware alignment protocol. Pair-wise correlation and principal component analyses on each sample's gene expression profile will be used to determine the quality of the experiment, identify batch effects and other systematics. Differential expression between samples (young and old, and after acarbose and after placebo) will be determined, using a negative binomial model approach such as that implemented in the DESeq package. Genes that show an adjusted p-value of less than 0.05 and a fold change greater than 2 will be selected for further scrutiny between placebo and acarbose conditions. Furthermore, our RNA-seq data will permit us to identify splice variants between the experimental conditions. The differential gene list will be processed with Ingenuity Pathway Analysis and GoStat, allowing us to identify dysregulated pathways and common gene ontology terms differentiating the acarbose transcriptome for the tissue types under scrutiny. Finally, the entire differential expression profile will be processed using the Broad's Gene Set Enrichment Analysis platform against over 10,000 curated gene lists, to provide additional regulatory perspectives on the data. These analyses are considered exploratory in nature and will be used to inform future tests that may target specific gene expression pathways. It will also allow us to make collaborative associations with phenotypes, although these associations will be complex considering the numerous potential age-delaying effects that may occur, some of which may be independent of the measured physiologic parameters.

Insulin sensitivity, biomarkers, etc.: Differences in mean acarbose vs. placebo treatment outcomes (insulin sensitivity, inflammatory biomarkers) will be tested for significance using paired t-test or Wilcoxon test (for non-parametric data). A two-tailed alpha level of 0.05 will denote statistical significance.

miRNA analysis:

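### Sub-aim 1's correlation of changes across men can be non-zero even if acarbose is inert; adjust it for sequence and report it as co-variation (minor, cheap improvement)

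*Combined protocol and SAP*

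**What the plan says.** Section A presents Sub-aim 1 as a secondary analysis: "we plan to assess the relationship between changes in gene expression with selected phenotypic variables and biomarkers". The C.2.2 heading repeats it: "To assess the relationship between changes in gene expression with selected phenotypic variables and biomarkers". Section B gives the nearest thing to a method: "We plan to correlate changes in transcription (muscle and fat RNAseq), post-translational regulation (miRNA) and gut microbiome with changes in clinical metabolic outcomes", and the sentence goes on to inflammatory markers. None of these places defines a change, names a coefficient, includes a sequence or period term, or gives a reference value for the correlation.

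C.3.2 gives a test for the clinical variables but not for the correlations: "Differences in mean acarbose vs. placebo treatment outcomes (insulin sensitivity, inflammatory biomarkers) will be tested for significance using paired t-test or Wilcoxon test", with the threshold "A two-tailed alpha level of 0.05 will denote statistical significance". Of the expression data it says "It will also allow us to make collaborative associations with phenotypes", and the same sentence warns that these associations will be complex.

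On timing, C.1 says that at visit 4 "a standard mixed meal test (SMT) will be conducted and muscle and adipose tissue biopsies will be performed", and visits 5-6 repeat visits 3-4. The schedule table marks biopsy, meal test, miRNA and stool at visits 4 and 6 only. C.2.1, however, mentions baseline biopsies. The stool paragraph of C.2.2 gives visits 4 and 6 in one sentence, and a baseline sample plus visit 4 in another. No baseline meal test is scheduled.

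C.3.1 acknowledges possible carry-over after the two-week washout, plans a separate look at men treated first, and adjusts for physical activity or weight only if these change significantly.

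**The concern.** Each man contributes one end-of-treatment visit on acarbose and one on placebo. His change is therefore the difference between two single days. Anything that moves a transcript and a clinical marker together on a given day, such as a minor infection, enters both differences. So does anything that moves both between the first and second period. A drug effect of the same size in every man is a constant and drops out of the correlation.

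Randomisation and blinding protect the mean acarbose-placebo contrast. They do not protect a correlation of differences across men. If these correlations were read as links between the drug's effect on expression and its effect on metabolism, natural fluctuation could be mistaken for mechanism. That matters because C.3.2 intends the expression analyses to inform later tests of specific pathways.

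**Working it through.** The plan gives no correlation, effect size or power for Sub-aim 1, so there is no figure to reproduce.

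**Inputs from the documents.** C.3.2: "We plan to enroll up to 30 older male subjects in a cross-over design (30 data points per treatment"), so n = 30 with one value per man per treatment. The two-sided 0.05 level is stated in C.3.2 for the clinical comparisons and is assumed here for the correlation.

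**Inputs assumed (not in the documents).** The same-visit, within-man correlation ρw is taken from 0 to 0.5. The period effect π shared by both measures is taken from 0 to 1 within-man SD. Men are split 15 per sequence.

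**Formula.** Let D = acarbose minus placebo, with within-man SD 1. Let τ be the SD of individual drug response and ρd the correlation of those responses between the two measures. Then

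corr(Dx, Dy) = (2ρw + πxπy + ρdτxτy) / √[(2 + πx² + τx²)(2 + πy² + τy²)].

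The mean drug effect does not appear. An inert drug means mean effect 0 and τ = 0.

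**Inert drug, no period effect.** The formula reduces to 2ρw/2 = ρw. At n = 30 the critical |r| is 2.048/√(28 + 2.048²) = 0.361. Fisher-z check for ρw = 0.3: atanh(0.3) × √27 = 0.310 × 5.196 = 1.61, and Φ(1.61 − 1.96) ≈ 0.36. Simulation of 20,000 trials gives:

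| ρw | share of trials with p<0.05 |
|---|---|
| 0 | 5% |
| 0.1 | 8% |
| 0.2 | about 18% |
| 0.3 | 37% |
| 0.5 | 83% |

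Adding a uniform effect of 2 SD to both measures leaves this unchanged: 5% at ρw = 0 and 37% at ρw = 0.3.

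**Inert drug, ρw = 0, shared period effect.** The formula reduces to π²/(2 + π²). For π = 1 this is 1/3 = 0.33.

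| π (SD) | expected r | p<0.05, unadjusted | p<0.05, adjusted for sequence |
|---|---|---|---|
| 0.25 | 0.03 | 5% | 5% |
| 0.5 | 0.11 | 9% | 5% |
| 0.75 | 0.22 | 22% | 5% |
| 1.0 | 0.33 | 47% | 5% |

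**Both sources.** With ρw = 0.3 and π = 0.5, r = (0.6 + 0.25)/2.25 = 0.38 and rejection is 56%. Adjusting for sequence brings it to 36%. The period part is removed and the natural co-variation stays.

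**The reverse error.** Genuinely linked responses (τ = 1, ρd = 0.6) give r = 0.6/3 = 0.20 when ρw = 0, but (−0.6 + 0.6)/3 = 0 when ρw = −0.3. A correlation near zero does not rule out a drug link either.

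**The case against.** **The correlation need not be non-zero.** A reader might infer that it always is under an inert drug. The documents do not support that. With no same-visit correlation and no shared period effect, the expected r is 0 and rejection is 5%. A non-zero ρw is plausible because biopsy and meal test share a visit, but it is an assumption. The 83% belongs to one transcript-marker pair at an assumed 0.5.

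**The plan does not claim proof.** A reader might also infer that the protocol treats the correlation as showing a drug-induced link. It does not say so. It speaks of assessing a relationship, calls the expression analyses exploratory and warns that the phenotype associations are complex. This stands, and it limits the severity.

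**Acarbose minus placebo is inferred.** It comes from the schedule and is not written for this analysis. C.2.1 and C.2.2 mention baseline biopsy and stool samples, which must be reconciled with the schedule. With no baseline meal test, the inference holds for the meal-test outcomes.

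**A gene filter might come first.** C.3.2 selects genes by adjusted p-value and fold change for further scrutiny, and the text does not say whether the correlations are limited to these. It would not help: selecting on a mean shift does nothing to a correlation that does not depend on the mean.

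Exploratory status does excuse low power and multiplicity. It does not settle what the correlation measures, and a larger sample would not either: with ρw above zero, rejection rises with n.

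**Conclusion.** The point holds as a minor one. As planned, the correlation of changes cannot by itself separate individual drug response from same-visit co-variation and shared period effects. With an inert drug and n = 30, false linkage ranges from 5% to 83% over assumed within-man correlations of 0 to 0.5, and from 5% to 47% over shared period effects of 0 to 1 SD. These ranges rest entirely on assumed inputs.

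It would go too far to say that the trial's data could never address the question. Comparing the same-visit covariance on acarbose with that on placebo holds the 5% level under an inert drug. It also assumes that drug response is independent of a man's usual level, and its power at n = 30 is only about 12-25% in the scenarios computed (τ = 1, ρd 0.6 to 0.9).

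Sub-aim 1 is secondary and exploratory, and the Aim 1 mean comparison is untouched.

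**What to change.** In C.2.2 and C.3.2:

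- Define change as the acarbose-minus-placebo difference, and reconcile the baseline biopsy and stool statements with the schedule table.
- Compute each correlation within treatment sequence, as a partial correlation adjusting for sequence. This returns the period-driven 47% to 5%.
- Since 36% remains at a within-man correlation of 0.3, state that the results describe within-man co-variation and are not evidence that acarbose-induced expression changes drive or track clinical changes.

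Two tempting additions should not be offered as proof of a drug link. Restricting to transcripts with a mean acarbose-placebo difference leaves natural co-variation in place. Benchmarking against non-responsive transcripts works only if these co-vary naturally with the marker to the same degree, which matching on expression level does not ensure.

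The cost is a few lines of text, a little programming and one degree of freedom, with no new data. Fewer associations will be attributed to acarbose.

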Informed consent	x							
		Diananaa		Diamanaa				
OGTT & eligibility labs (\$)	X	Dispense study meds (treat- ment A)		Dispense study meds (treat- ment B)		Start treatme nt B		
Safety monitoring (*)			X				X	
serum for miRNA				X				X
Stored samples for biomarkers,				Х				X

4	EINSTEIN				
Albert Einstein College of Medicine					

Vital signs, height, weight	Х	X	X	X		X	X
History	х	Interim history	Interi m histor y	Interim history		Interim history	Interim history
Physical exam (**)	X	X					
Standard meal test (#)				х			X
Muscle & adipose tissue biopsy				X			X
Fecal collection				Х			X

- (\$) eligibility labs include OGTT, Cr, AST/ALT, CBC, urinanalysis
- (*) safety monitoring includes recording of AEs and labs (Cr. AST/ALT)
- (#) standard meal test includes: fasting hsCRP, IGF-1, HbA1c and adiponectin, lipid profile, serum microRNA, Fasting and every 30 minute glucose, insulin levels.
- Fasting and 2 hour samples stored for possible future use.
- (**) Physical exam can be performed during visit 1 or visit 2.

Consent Process:

For this clinical investigation we will be consenting the research participants in compliance with our local IRB policy, Department of Health and Human Services (HHS) regulations for the Protection of Human Research Subjects (45 CFR 46) and FDA regulations (21 CFR 50 & 56).

For an initial phone screening we will be using a phone consent form that contains also HIPAA language. We will ask for permission to collect personal information and if they agree to be contacted for other future studies.

During the screening visits in the Clinical Research Center (CRC), subjects will sign the current IRB-approved and stamped consent document.

Prior to the adipose and muscle biopsies (visit 4 and visit 6), the physician performing the procedures will obtain consent using a standard Montefiore procedural consent, again detailing the procedures and expected risks.

Study visits:

Screening visit (Visit 1): Following informed consent, a history, vitals, anthropometrics, and screening labs, including OGTT, will be obtained.

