Visit 2: Subjects for the study intervention who meet eligibility criteria (see below) will be invited to enroll in the study. Study medication (Treatment A: acarbose or placebo, double-blind) will be dispensed for the following 10 weeks. Since flatulence and abdominal discomfort are common with acarbose, slow titration is often needed. Subjects will be instructed to begin with 1 capsule with the first bite of one meal each day, and will be given instructions on titrating study medication as tolerated to 2 capsules with each meal (breakfast, lunch, and dinner) after 2 weeks. Subjects unable to tolerate any study med, will be withdrawn from the study. Subjects will be contacted every other week by phone to assess adherence and to adjust dosing if necessary. Physical exam will be performed in visit 1 or visit 2 by a licensed study physician to confirm no major physical limitations or illness prior to randomization.

Visit 3: Monitoring visit. This visit will be a visit to assess compliance and dose escalation. Subects who able to tolerate 2 capsules three times daily, will be provided with a higher dose capsule, and instructions to titrate to 2 (higher dose) capsules three times daily. If they are only able to tolerate 1 capsule three times daily of the lower dose, they will be given more of the lower dose capsule to take for the remainder of the treatment period. Interim history will be performed. Liver function tests will be checked. A fecal microbiome stool collection kit and instructions will be provided

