Men; age >60 years with IFG or IGT based on 75g OGTT (fasting plasma glucose 100 - 125 mg/dl and/or 2-hr glucose between 140 - 199 mg/dl,), or mild untreated diabetes based on OGTT (fasting plasma glucose 126 - 139 mg/dL and/ or 2 hr glucose between 200 - 249, with a hemoglobin A1c <6.5). We chose these inclusion criteria in order to study subjects who have evidence of impaired glucose regulation, but do not meet criteria for pharmacologic treatment of diabetes.

Exclusion:

1. Serious chronic or acute illness: cancer, clinically significant congestive heart failure, COPD, inflammatory conditions, eGFR<45, active liver disease, poorly controlled hypertension, epilepsy, recent (within 3 months) CVD event (MI, PTCA, CABG, stroke), inflammatory bowel disease; history of bariatric or other gastric surgery, cigarette smoking, serious substance abuse.

- 3. Hypersensitivity to acarbose or any component of the formulation
- 4. Patients taking anti-coagulant medications (e.g., warfarin) or anti-platelet drugs are excluded because of the increased risk of bleeding from muscle and fat biopsies. People taking aspirin for primary prevention who can safely stop the medication for 7 days may be included.
- **C.1.4. Acarbose dose and formulation:** Studies have demonstrated the ability of acarbose to delay or prevent the onset of diabetes in people with impaired glucose intolerance or pre-diabetes. The usual therapeutic dose ranges from 150 mg to 300 mg a day. For this study, we plan to use the maximum tolerated dose of up to 300 mg daily of acarbose. The drug will be introduced at 25mg daily, to be taken with the first bite of a meal. This will be increased to 25mg three times daily, then doubled in 1-2 weeks to 50mg 3 times daily as tolerated, and further doubled in another 1-2 weeks to 100mg 3 times daily as tolerated. Participants may continue to actively participate in the study with a reduced, but tolerable, dose of acarbose (minimum 75 mg daily). Capsules that contain 25mg acarbose or a similar appearing placebo containing lactose will be prepared by the Weiler Hospital research pharmacy.
- **C.1.5. Duration of treatment:** We propose 2x 10-week duration of treatment (4 weeks titration, 6 weeks maximal dose) with a 2-week washout between treatment periods. We have reasoned that this time frame should be sufficient to see effects on gene expression.

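### Minor: each man has one scheduled liver test on acarbose, at treatment week 4, and none in treatment weeks 5–10; adding AST/ALT and creatinine to the Visit 4 and 6 blood is a cheap improvement

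*Combined protocol and SAP*

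**What the plan says.** The schedule table in C.1 marks safety monitoring at two visits, and its footnote defines the content: "safety monitoring includes recording of AEs and labs (Cr. AST/ALT". The table is partly broken in the text available, but the visit descriptions confirm the positions. Visit 3, at week 4, carries the liver test: "Interim history will be performed. Liver function tests will be checked". The Visit 4 description has no such test, and for Visits 5 and 6 the text is "The procedures in visits 3-4 will be repeated". After screening, the liver tests therefore fall at Visit 3 (week 4) and Visit 5 (week 16).

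Blood is drawn at Visits 4 and 6 for the meal test and stored samples. The Visit 4 text says "Fasting and 2hour blood samples will be collected for analyses noted above", and the footnote lists the content: "standard meal test includes: fasting hsCRP, IGF-1, HbA1c and adiponectin, lipid profile, serum microRNA, Fasting and every 30 minute glucose, insulin levels". AST/ALT and creatinine are not in it. C.1.6 names liver profiles among the laboratory's assays but gives no visit for them.

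On dose, the Visit 3 text says that men who tolerate the first capsule "will be provided with a higher dose capsule, and instructions to titrate to 2 (higher dose) capsules three times daily". C.1.4 allows a faster course, with the 50 mg step "further doubled in another 1-2 weeks to 100mg 3 times daily as tolerated". C.1.5 gives 4 weeks of titration and 6 at the highest dose.

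D.1.1 puts mild transaminase elevations at up to 14% and those above 3 x ULN at 3%. It describes them as usually dose related and reversible, and cites a quarterly testing recommendation as the reason for the safety-visit test.

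**The concern.** The single on-acarbose test comes 4 weeks into a 10-week exposure, and most or all of the time at the top dose lies after it. Since D.1.1 ties elevations to dose, this is where a late check would be most informative.

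No later scheduled test closes the gap. In acarbose-first men the next value is taken well after the drug has stopped, when a reversible rise may have gone. In placebo-first men nothing follows. Those men also begin acarbose on a liver value from the middle of the placebo period.

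At stake is a silent elevation: a man with a normal week-4 value and no symptoms whose enzymes rise later. The fortnightly calls and interim histories depend on symptoms, and the 24-hour review in D.1.3 helps only if a sample was sent.

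**Working it through.** **Inputs.** From C.1: Visit 3 at week 4, Visit 4 at week 10, start of treatment B at week 12, Visit 5 at week 16, Visit 6 at week 22. From C.1.4 and C.1.5: 25 mg capsules, a maximum of 300 mg/day, 10 weeks per period, 2 weeks of washout. From C.3.2: up to 30 men, each scheduled to receive acarbose. From D.1.1: 14% and 3%.

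**Plan's own figure.** 10 + 2 + 10 = 22 weeks, as stated in C.1.

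**Timing of liver tests.**

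| | Acarbose first (weeks 0–10) | Placebo first (acarbose weeks 12–22) |
|---|---|---|
| Treatment week of on-acarbose test | 4 − 0 = 4 | 16 − 12 = 4 |
| Acarbose weeks after that test | 10 − 4 = 6 | 22 − 16 = 6 |
| Next scheduled test | week 16, i.e. 16 − 10 = 6 weeks off acarbose | none |
| Age of last on-study value when acarbose starts | screening value; interval not stated | 12 − 4 = 8 weeks |

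In both sequences 6/10 = 60% of the acarbose weeks follow the only on-acarbose test.

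**Share of top-dose weeks after the test,** for a man who reaches 300 mg/day and stays there to week 10:

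- Fastest course under C.1.4, taking the once-daily 25 mg step as 0 weeks because its length is not given: 300 mg/day from week 1 + 1 = 2. That leaves 4 − 2 = 2 weeks before the test and 6 after; 6/8 = 75%.
- Slowest two steps under C.1.4 (2 + 2 = week 4), or C.1.5: 0 weeks before, 6 after; 6/6 = 100%.
- Visit 3 text: the step-up starts at the visit where blood is taken, so 100%. The dose at the test is then at most 2 x 25 x 3 = 150 mg/day, if the lower-dose capsule is 25 mg.

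The range needs the no-step-down condition. A man at 300 mg/day from week 2 who steps down at week 5 has 1 of 3 top-dose weeks (33%) after the test.

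**Scale.** Applying the D.1.1 rates to 30 men: 30 x 0.14 = 4.2 with any elevation and 30 x 0.03 = 0.9 above 3 x ULN, over the whole acarbose exposure. The documents do not give the share s that arises after week 4. With s from 0 to 1, the ranges are 0 to 4.2 and 0 to 0.9.

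**With tests added at Visits 4 and 6.** On-acarbose tests per man go from 1 to 2 (treatment weeks 4 and 10). Acarbose weeks after the last on-acarbose test go from 6 to 0. The pre-acarbose value in placebo-first men goes from 8 weeks old to 12 − 10 = 2.

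**The case against.** The strongest reply is that no standard in the documents is missed. D.1.1 cites quarterly testing. Each 10-week period is shorter than a quarter and contains a test, and the two on-study tests are 16 − 4 = 12 weeks apart. A reader might infer from the gap that the plan breaches its own monitoring rationale; it does not, and this part of the reply stands in full.

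Second, a test at treatment week 10 falls as dosing ends. A reader might expect it to protect men during weeks 5–10. It cannot: that would need a draw around treatment weeks 6–8. D.1.1 also calls the elevations reversible, and acarbose stops at the end of the period anyway. What remains is detection and follow-up, plus a recent value before treatment B.

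Third, safeguards exist. Men with active liver disease are excluded, calls and interim histories continue, and the Visit 4 text provides that "Additional interim safety and/or adherence visits will be conducted if indicated". A raised week-4 value could trigger such a visit. The gap is confined to men with a normal week-4 value and no symptoms.

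Fourth, the 8-week-old value has no comparator. The documents set no maximum age for a liver test before dosing and do not give the interval from screening to Visit 2, so placebo-first men are not shown to be worse placed than acarbose-first men.

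None of this changes the count of tests or the low cost of adding two.

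**Conclusion.** The point holds as a minor, inexpensive improvement. Each man has one scheduled on-acarbose liver test, at treatment week 4, and none in treatment weeks 5–10. No scheduled test at the end of exposure makes up for this in either sequence.

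The benefit is small and could be nil: 0 to 4.2 men with any elevation, and 0 to 0.9 above 3 x ULN, arising after week 4. This assumes 30 men all take acarbose and that the D.1.1 rates, which are tied to no dose or duration, apply to 10 weeks at up to 300 mg/day. The 75% to 100% range for top-dose weeks applies only to men who reach 300 mg/day and do not step down.

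Two stronger readings should be avoided. One is that the week-4 test always precedes the top dose: the Visit 3 text implies this, but under C.1.4 some men could already be at 300 mg/day. The other is that 4.2 elevations would be missed: that figure is a ceiling for the whole exposure, and the existing test may find some or all of them.

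**What to change.** Keep the tests at Visits 3 and 5. Add AST/ALT and creatinine to the blood already drawn at Visits 4 and 6, and mark the safety-monitoring row there. Do this in both periods, since blinding rules out testing acarbose periods only.

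State a limit in advance, for example 3 x ULN. Review the Visit 4 result before treatment B starts at week 12; the 24-hour review in D.1.3 fits easily into the 2-week washout. Hold treatment B if a value exceeds the limit, and repeat values above it until they resolve, including after Visit 6.

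Cost:

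- A schedule amendment and some staff time for review.
- Up to 2 x 30 = 60 extra panels, 30 of them after placebo, with no new scheduled draw.
- Repeat draws after acarbose, at an assumed 1 to 3 per affected man: 0 to 0.9 x 3 = 2.7, about 3, with a 3 x ULN limit. If any elevation is repeated, 0 to 4.2 x 3 = 12.6, about 13.
- Repeat draws after placebo, which cannot be estimated because the documents give no placebo rate.
- A shifted calendar for any man whose treatment B is held.
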